Diabetic foot ulceration (DFU) is a common and largely preventable complication. [1] While most of these ulcers can be treated successfully, some will persist and become infected. Ultimately, nearly one fifth of patients with infected lower-extremity diabetic ulcers will require amputation of the affected limb, resulting in staggering costs for both the patient and the healthcare system. Prevention by identifying people at higher risk is the key for better clinical management of such patients. It is not uncommon for patients suffering from diabetes to have concomitant lower extremity edema or even venous insufficiency[2-4] and they subsequently may benefit from graduated compression[5-7]. However, because of the common association of peripheral arterial disease (PAD) in patients with diabetes[8-10], most clinicians are reluctant to apply compressive dressings in fear of exacerbating the symptoms of PAD and the possible resulting gangrene[11].

Unfortunately, this area has received comparatively little attention from industry, academia, or insurance providers. A novel micro-mobile intermittent pneumatic foot compression device (AVEX Footbeat, Inc.) offers alternative means providing lower extremity compression. This device is portable and can be used in ambulatory settings providing increased venous blood and relief from concomitant lower extremity edema.

Section D: Purpose and Objectives

The purpose of this study is to conduct an observational study with N=30 patients to assess whether this micro-mobile foot compression device can help reduce lower extremity in patients with both diabetes and lower extremity edema without compromising the vascular supply.

The main purpose of this study is to determine if the device lessens edema. This study will also evaluate a new research device to see if it may help prevent diabetic foot ulcers. Additionally, it may potentially help delay progression of foot disease and produce a better quality of life by providing a better blood flow to foot and ankle.

Primary Endpoints: Reduction in lower extremity edema at 4 weeks of continuous device usage. Peripheral edema will be measured at baseline, 48 hours, 1 week and 4 weeks. Peripheral edema will be directly measured by traditional volume change assessment and indirectly by skin perfusion pressure assessment.

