Secondary Endpoints: 1) Improvement in balance and fall risk as measured at baseline and 4 weeks. 2) 48 Hours of continuous daily physical activity using a validated body worn sensor as measured at baseline and 4 weeks. 3) Gait assessment at baseline and 4 weeks.

Specific Aim and Hypothesis

Aim 1. To assess the effectiveness of a micro-mobile foot compression device that provides mild compression to help reduce peripheral edema as compared to baseline in patients with both diabetes and lower extremity edema in a four-week observational clinical trial of 30 patients.

Hypothesis 1: The micro-mobile foot compression device will result in edema reduction when compared to baseline peripheral edema for the study population.

Aim 2. To assess the effect of micro-mobile foot compression device on the macro and micro lower extremity circulation as measured by Ankle Brachial Index (ABI) and Skin Perfusion Pressure (SPP) Measurements.

Hypothesis 2: The micro-mobile foot compression device will help improve macro and micro- circulation in the lower extremity of patients with diabetes and lower extremity edema as compared to baseline. We expect to see positive changes in ABI and SPP measurements.

Aim 3. To assess the effect micro-mobile foot compression device on the quality of life quantified using the validated, international quality of life assessment survey SF12, fear of falling quantified by FES-I, and risk of falling assessment quantified by gait, balance and spontaneous daily physical activity of patients with diabetes and lower extremity edema.

Hypothesis 3. The micro-mobile foot compression device will improve the quality of life, lower the risk of falling, lower fear of falling, and improve activity level of patients as compared to baseline assessments.

Section E: Protocol Risks/Subjects

E1. Risk Category

Category 2: Research involving greater than minimal risk, but presenting the prospect of direct benefit to the individual subjects.

E2. Subjects

Gender:

Both

Age:

Adult (18-64 yrs), Geriatric (65+ yrs)

Ethnicity:

All Ethnicities

Primary Language:

English, Spanish

Groups to be recruited will include:

Patients

Which if any of the following vulnerable populations will be recruited as subjects?

Vulnerable populations require special protections. How will you obtain informed consent, protect subject confidentiality, and prevent undue coercion?

E3. Pregnant woman/fetus

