Will pregnant women and/or fetuses (as described in 45 CFR 46 Subpart B) be enrolled in the research?

No

E4. Neonates

Will neonates of uncertain viability or nonviable neonates (as described in 45 CFR 46 Subpart B) be enrolled in the research?

No

E5. Children

Will children be enrolled in the research?

No

Section F: Design/Procedure

F1. Design

Select one category that most adequately describes your research:

c) Pilot

Discuss the research design including but not limited to such issues as: probability of group assignment, potential for subject to be randomized to placebo group, use of control subjects, etc.

In this proof of concept, intent to treat trial, 30 consecutive patients with diabetes and lower extremity edema will be recruited from the outpatient clinic at Baylor College of Medicine. Patients will be consented per the local Institutional Review Board's guidelines and approval for this study.

Inclusion Criteria:

a) Males or females age 18-90 years old with history of type 1 or 2 diabetes and the ability and willingness to provide Informed consent b) Patients at risk of developing diabetic foot ulcers c) Patient is willing to participate in all procedures and follow up evaluations necessary to complete the study. d) Patients who have undergone lower extremity surgery / amputation may be enrolled into the study at the clinical judgment of the Investigator

Exclusion Criteria:

a) Patients with severe peripheral vascular disease (ABI or ankle brachial systolic pressure index <0.5) b) Patients with diabetic foot ulcers in the plantar foot region c) Patients with active wound infection, or untreated osteomyelitis d) Patients currently on immunosuppressive drugs. e) Pregnant or breastfeeding females. (standard urine pregnancy done on women during physical exam procedures) f) Acute fractures of the foot g) Acute heart failure h) Participation in an interventional Study within the last 30 days i) Non-ambulatory or unable to stand without help or walk a distance of at least 6 feet without assistance. k) Patients with major foot amputation. j) Patients who are unable or unwilling to participate in all procedures and follow up evaluations h) Patients with major foot deformities which won't fit in the diabetic shoes

F2. Procedure

Following is a summary of study procedures:

Study Day 0 (initiation), Visit 1 The following baseline values will be assessed and documented.

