Other assessments: Other relevant assessments are Demographic/Health questionnaire, the Mini-Metal State Exam, the mobility-tiredness scale, Barthel Index, Depression Scale, fear of falling (Short-Falls Efficacy Scale – International)[25], quality of life (SF-12 Health Survey)[26], Fried Frailty Criteria, Foot Questionnaire, Pain Assessment, Fall Log and Contact Agreement, Physical activity log, follow-up questionnaire, and Shoe-fit test

AVEX insole: The AVEX insole will be given to the subject. The research personnel will adjust the clutching reel (BOA technology) in order to ensure a comfortable shoe fit. The research personnel will also provide device education to the subject and will answer any questions which may arise.

Study Day 1, Visit 2 48-hour follow up: All participants will be asked to return to clinic approximately 48 hours after visit 1. In this visit, (1) any adverse events will be assessed; (2) activity measurement (body sensor) will be returned; (3) AVEX insole data will be downloaded to ensure operability and patient compliance; and (4) further device education will be provided in case any issues have risen

Study Day 2, Visit 3 1-week follow-up: All participants will be asked to return to clinic approximately 1 week after visit 1. In this visit, (1) any adverse events will be assessed; and (2) AVEX data download to ensure operability and patient compliance. Device education will be provided if needed. The subject will be asked to return the device at their next visit. Similar assessments performed during visit 1 may be performed again during this visit.

Study Day 3, Visit 4 4-week follow-up: All participants will be asked to return to clinic approximately 4 weeks after visit 1. In this visit, outcome assessment using similar assessments described for Study Day 0 will be performed. In addition, benefit and user-friendliness of the AVEX insoles and Boa Technology 'Clutch Reel' will be assessed using a questionnaire. The subject will return the device back to the research personnel.

Patients will be asked to wear a comfortable shirt which holds a small activity monitor (PAMSys) for a period of 48 Hours (2 days). Patients will be requested to return this device via a pre-paid FEDEX envelope

Study Day 4, Visit 5 Three month follow-up: All participants will be contacted by the study coordinator approximately three months post the last study visit (Visit 4) to document potential incident of diabetic foot ulcer or falls.

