The researchers will take digital photographs of you and videotape you and your feet during the study to monitor progress or deterioration (worsening) due to intervention. This is done using a normal digital camera for visual images and a thermal (heat sensitive) camera for thermal images. Both these methods are non-invasive. **We will NOT blur your face out in the photographs/videos. While we do all our efforts to mask your face in some cases (for example, journal policy) this may not be practical. We will only use videos and photos of you for scientific presentations or scientific publications. Initial your decision below.

I agree to have my photographs/videotape presented in scientific presentation or scientific publication

I do NOT agree to have my photographs/videotape presented in scientific presentation or scientific publication

Please provide below your Emergency contact information:

Contact name: _____

Relationship: _____

Phone number: _____

Section G: Sample Size/Data Analysis

G1. Sample Size

How many subjects (or specimens, or charts) will be used in this study?

Local: 50 Worldwide: 50

Please indicate why you chose the sample size proposed:

This is an initial proof of concept pilot study. The results of this study will allow for the calculation of an appropriate sample size for a larger proof of superiority (over current standard of care) trial.

G2. Data Analysis

Provide a description of your plan for data analysis. State the types of comparisons you plan (e.g. comparison of means, comparison of proportions, regressions, analysis of variance). Which is the PRIMARY comparison/analysis? How will the analyses proposed relate to the primary purposes of your study?

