Statistical Analysis - This study includes three hypotheses. To examine whether the proposed micro-mobile foot compression device will result in a edema reduction compared to the baseline (H1), we will use ANOVA and Fisher's exact tests for intra-subject rate of edema reduction using the outcome explained before. Multivariate and multiple linear regression test will be used for testing the effects of confounding factors including age, gender, BMI, foot insensitivity, etc. Additional, paired t-test will be used to examine whether amount of edema reduction at the end of study is significant compared to baseline. We will use Pearson correlation of coefficient and Fisher's exact tests to examine whether severity of neuropathy has any significant association with the rate of edema reduction. Finally, we will use multiple linear regression model to examine whether subject's level of activity, BMI, ABI, Skin perfusion pressure, and micro-mobile foot compression device are independent predictors for the rate of edema reduction.

To examine whether the proposed sock will help improve macro and micro-circulation in the lower extremity of patients (H2), we will use the similar analytical plan explained above by considering change in Skin perfusion pressure and ABI as dependent variables. For identifying the predictors, we will use multiple linear regression model and Anova (n-way). The independent variables will be severity of neuropathy quantified using Semmes Weinstein Monofilament, the level of activity, BMI, and age.

To examine whether the proposed socks will improve the activity level and quality of life (H3), we will use ANOVA multivariate test. The dependent variables will be number of total steps per day, duration of walking and standing, duration of longest episode of walking (i.e. continuous walking without stop), number of walking episode, duration of sit-to-stand and stand-to-sit postural transition, and SF12. We will use multiple linear regression model and multi-variant test to examine the effect of confounding parameters such as weather condition, BMI, age, etc.

Section H: Potential Risks/Discomforts

H1. Potential Risks/Discomforts

Describe and assess any potential risks/discomforts; (physical, psychological, social, legal, or other) and assess the likelihood and seriousness of such risks:

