Explain why the waiver will not adversely affect the privacy rights and the welfare of the research subjects.

Patients will receive the same standard of care regardless to whether they participate or not. These patients will be clinic or established patients of the PI. Therefore, they already consent to a review of their charts at the time they are seen in clinic the first time and before they are even added to the PI's patient database.

Explain why the research could not practicably be conducted without the waiver and could not practicably be conducted without access to and use of the protected health information.

If we are not allowed to search our patient's records, we cannot identify and recruit the patients that are eligible for the study. This research will not affect the subject's care as they are receiving the standard of care.

Describe how an adequate plan exists in order to protect identifiers from improper use and disclosure.

The use or disclosure of PHI involves no more than minimal risk to the individuals and the waiver will not adversely affect the privacy rights and the welfare of the individuals as subjects will receive the same standard of care regardless of whether or not they participate in the study.

Describe how an adequate plan exists in order to destroy identifiers at the earliest opportunity consistent with conduct of the research, unless there is a health or research justification for retaining the identifiers or such retention is otherwise required by law.

We will destroy identifiers at the earliest opportunity consistent with conduct of the research absent a health or research justification for retaining them or a legal requirement to do so. The use or disclosure of PHI involves no more than minimal risk to the individuals and the waiver will not adversely affect the privacy rights and the welfare of the individuals. PHI is not disclosed to any other person or entity except for the authorized oversight of the research study by the PI and the clinical database administrator. The Division uniformly adheres to all patient and patient data security and confidentiality rules and regulations set forth by the College.

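### The one-arm change from baseline cannot isolate the device effect or supply the effect size for a superiority trial, and G1 does not say which pilot results will be used

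*Combined protocol and SAP*

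**What the plan says.** **Design.** F1 describes a proof-of-concept pilot in which "30 consecutive patients with diabetes and lower extremity edema will be recruited from the outpatient clinic"; Aim 1 places it "in a four-week observational clinical trial of 30 patients". F2 states for Visit 1 that "The AVEX insole will be given to the subject". No control group, run-in or repeat baseline is described. Section D schedules edema at baseline, 48 hours, 1 week and 4 weeks. The device is returned at Visit 4, and the three-month contact covers only ulcers and falls, so there is no later off-device edema reading.

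**Other care.** Section J1 says: "This research will not affect the subject's care as they are receiving the standard of care". The background section says of patients with diabetes and edema or venous insufficiency that "they subsequently may benefit from graduated compression", then adds that most clinicians hesitate to use compressive dressings because arterial disease is common. The exclusion criteria neither bar compression or edema-related medication nor require them to be stable.

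**Hypothesis and analysis.** Hypothesis 1 reads: "The micro-mobile foot compression device will result in edema reduction when compared to baseline peripheral edema for the study population". G2 tests it within patients, including a paired t-test of the end-of-study change, and plans regression for "testing the effects of confounding factors including age, gender, BMI, foot insensitivity, etc". A further regression lists activity, BMI, ABI, skin perfusion pressure and the device itself as candidate independent predictors of edema reduction.

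**Use of the results.** G1 gives one reason for the sample size: the pilot will permit the "calculation of an appropriate sample size for a larger proof of superiority (over current standard of care) trial". It names no input for that calculation and no target difference.

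**The concern.** Two inferences go further than the design can carry.

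The first is attribution. Hypothesis 1 says the device will produce the reduction, but the only contrast is each patient against one earlier reading. A patient whose other edema treatment is started or intensified during the 4 weeks counts towards the device, and the plan names no data item that would reveal it. Adjusting for age, gender, BMI or insensitivity may explain which patients change more. It cannot separate the average change from what would have happened anyway.

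The second is sizing. A superiority trial needs the difference between device and standard care. The pilot observes no standard-care change, so its mean change is not an estimate of that difference. Because G1 does not say which results will be carried forward, nothing stops the mean change from being used. If part of it would occur under standard care, the next trial would be too small.

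**Working it through.** **1. The plan's own figure.** G1 gives 50 subjects; Section D, Aim 1 and F1 give 30. No alpha, power, effect size or SD is stated, so neither number can be reproduced. Results below are shown for both where they depend on the pilot's size.

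**2. What the mean change estimates.** Let D be the device effect over standard care and S the mean change that would occur under standard care (other treatment, time trend, fluctuation). The pilot observes D + S. The superiority trial needs D. There is one observed quantity and two unknowns, and no arm or off-device period estimates S.

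**3. Consequence if D + S were used as the effect.** Assume two-sided alpha 0.05, planned power 80%, and equal SDs in both arms. Let f = S/(D + S). The planned standardised signal is 1.96 + 0.8416 = 2.8016, so

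- true power = Φ((1 − f) × 2.8016 − 1.96)
- required size relative to planned = 1/(1 − f)²

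| f (assumed) | Argument of Φ | True power | Size ratio |
|---|---|---|---|
| 0 | 0.842 | 80% | 1.00 |
| 0.20 | 0.281 | 61% | 1.56 |
| 0.30 | 0.001 | 50% | 2.04 |
| 0.50 | −0.559 | 29% | 4.00 |
| −0.20 | 1.402 | 92% | 0.69 |

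The last row is the case where edema would worsen under usual care: the mean change then understates D and the trial would be larger than needed. The documents give no value of f, and the pilot cannot estimate it.

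**4. Consequence for attribution.** Suppose the device has no effect but edema falls for other reasons by a given multiple of the SD of change (assumed values). The probability that the two-sided paired t-test is significant at 0.05 (noncentral t) is:

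| Non-device decline | n = 30 | n = 50 |
|---|---|---|
| 0.2 SD | 19% | 28% |
| 0.3 SD | 36% | 55% |
| 0.5 SD | 75% | 93% |

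**5. What the pilot can supply.** The 95% limits for an SD run from 0.80 to 1.34 times the estimate at n = 30 and from 0.84 to 1.25 times at n = 50. Retention and adherence are also observable; insole data are downloaded at Visits 2 and 3.

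**6. The device term in the regression.** All patients receive the device, so its indicator equals 1 for everyone and coincides with the intercept. Its coefficient cannot be estimated.

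**The case against.** The strongest reply is that this is an openly labelled pilot, that Aim 1 and Hypothesis 1 name baseline as the comparator, and that G1 speaks only of the study's results. All of that stands. An uncontrolled pilot is acceptable, and a trial can be sized from its SD, retention and adherence.

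Several stronger readings are tempting, but the documents do not support them:

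- **That the sponsor plans to use the before-after mean as the superiority effect.** G1 does not say so. The fault is that it leaves the inputs open.
- **That other edema treatment goes unrecorded.** Visit 4 repeats the Day 0 types of assessment, Visit 3 may do so, a follow-up questionnaire is listed without its content, and Section K includes medications among the data. The fair statement is that no section names compression or edema-related medication as a visit item or a covariate.
- **That compression is common in these patients.** The background section reports reluctance to use it, and the J1 remark on standard care is a privacy justification. Neither shows that edema treatment is changing.
- **That the mean change must overstate the effect.** Edema may worsen under usual care. Regression to the mean is also of unknown size, because the listed inclusion criteria set no edema threshold.
- **That adjustment covers only fixed baseline traits.** The G2 list is open-ended, and the last H1 model adds activity, ABI and skin perfusion pressure, which are measured at baseline and due again at Visit 4. Without a comparator, this still does not separate the device from time or other treatment.

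**Conclusion.** The point holds as a limit on inference, not as a fault in running a one-arm pilot. With one pre-device reading, no comparator and continuing standard care, the 4-week change does not isolate the device effect and does not estimate the difference from standard care. G1 should say which results will size the next trial, and Hypothesis 1 should not assign cause.

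The size is conditional. Power of about 61%, 50% or 29% in place of 80% applies only if the mean change is used as the effect and 20%, 30% or 50% of it would also occur under standard care. Those fractions are assumptions, and a negative fraction reverses the direction. The constant device term needs no assumption: its coefficient is not estimable as written. The pilot remains usable, and the correction is inexpensive and worth making.

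**What to change.** 1. **G1.** State that the pilot supplies the SD of change, the baseline to 4-week correlation, retention and adherence. State that the superiority effect will be set from a minimum important difference, not from the pilot's mean change.
2. **Hypothesis 1 and G2.** Word the hypothesis and its conclusion as change from baseline during device use. Drop the device term from the regression, or replace it with downloaded device use. F2 names downloads at Visits 2 and 3 only, so add one at the Visit 4 return. Report any association with use as non-randomised.
3. **Visits 1 to 4.** Record compression use and edema-related medication. Keep all patients in the main analysis. Report how many changed other edema treatment and in which direction, and show the 4-week change with and without them as a descriptive sensitivity analysis. State that exclusion conditions on a post-baseline event: patients whose edema worsens may be the ones who intensify treatment, so leaving them out could remove device failures.

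Item 3 makes other treatment visible but does not measure time trend or fluctuation, so the limits in items 1 and 2 are still needed.

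**Cost.** Wording changes, one case-report item and one download at existing visits, and one descriptive table. The downside is a weaker causal claim.

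### The H1 and H2 predictor regressions of change do not list the outcome's own baseline, so a trait that merely tracks starting severity could be reported as an independent predictor

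*Combined protocol and SAP*

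**What the plan says.** All of this is in Section G2.

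- **H1, outcome and test of mean change.** The outcome is analysed by "ANOVA and Fisher's exact tests for intra-subject rate of edema reduction using the outcome explained before". In addition, a "paired t-test will be used to examine whether amount of edema reduction at the end of study is significant compared to baseline". The second test carries no covariates.
- **H1, covariates.** "Multivariate and multiple linear regression test will be used for testing the effects of confounding factors including age, gender, BMI, foot insensitivity, etc".
- **H1, predictors.** A further multiple regression asks whether "level of activity, BMI, ABI, Skin perfusion pressure, and micro-mobile foot compression device are independent predictors for the rate of edema reduction".
- **H2.** The plan reuses a "similar analytical plan explained above by considering change in Skin perfusion pressure and ABI as dependent variables". The predictors named there are monofilament neuropathy severity, activity, BMI and age.

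Baseline edema is not listed as a covariate for edema change, nor baseline SPP or ABI for its own change. ABI and SPP do appear in the H1 predictor list, but as predictors of edema and without a time point. Section F2 schedules edema, ABI and SPP assessment at Day 0, so the baseline values will exist. Sections D and F1 describe 30 patients, each compared with their own baseline and with no control arm. G1 gives 50.

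**The concern.** How much a swollen limb can shrink plausibly depends on how swollen it was at the start; the same may hold for SPP and ABI. A patient characteristic such as BMI or neuropathy may also go with starting severity. If both are true and baseline is left out, the characteristic picks up the effect of severity, and the report may name it as an independent predictor when it has no effect of its own.

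There is also a labelling problem. Age and gender, and for practical purposes BMI and foot insensitivity over four weeks, are the same at both ends of a within-patient difference. They can modify the change but cannot confound it.

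What is at stake is the credibility of the predictor findings, not the estimate of mean edema reduction.

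**Working it through.** The plan attaches no figure to these regressions and gives no alpha, SD, correlation or reliability, so there is nothing to reproduce. From the documents come n=30 (Sections D, F1), n=50 (G1) and the covariate lists (G2). Everything else below is assumed: two-sided 0.05, ordinary least squares, one trait X with no effect of its own on change, and three noise covariates, giving about the number of terms in the plan's models.

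**Step 1. Mean change.** Least squares with an intercept gives mean(y) = b0 + Σ bj·mean(xj). With centred covariates every mean(xj) is 0, so b0 = mean(y). In a numerical check both were −0.98274. The covariates describe who changes more; they do not move the mean change.

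**Step 2. Change depends on the baseline value.** Take equal variances, pre-post correlation ρ, and correlation r between X and baseline. Then cov(X, change) = −r(1−ρ) and var(change) = 2(1−ρ), so corr(X, change) = −r·√((1−ρ)/2). Baseline explains (1−ρ)/2 of the variance of change. At r=0.5, ρ=0.5 the correlation is −0.5·√0.25 = −0.25. False-positive rates for X, 5,000 runs per cell:

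| ρ | Share of change explained | r | corr(X, change) | n=30 without / with baseline | n=50 without / with baseline |
|---|---|---|---|---|---|
| 0.5 | 25% | 0.3 | −0.150 | 11.7% / 4.9% | 17.4% / 5.2% |
| 0.5 | 25% | 0.5 | −0.250 | 24.9% / 5.0% | 39.8% / 5.3% |
| 0.7 | 15% | 0.3 | −0.116 | 9.4% / 4.8% | 11.6% / 4.6% |
| 0.7 | 15% | 0.5 | −0.194 | 16.0% / 4.7% | 26.0% / 5.2% |
| 0.9 | 5% | 0.3 | −0.067 | 6.4% / 5.0% | 7.3% / 4.8% |
| 0.9 | 5% | 0.5 | −0.112 | 7.8% / 4.7% | 11.6% / 5.4% |

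At r=0 both models stay near 5%. Analysing percent change does not cure this: at r=0.5 and an assumed coefficient of variation of 15%, the rate without baseline is 10-26% (n=30) and 12-42% (n=50).

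**Step 3. The reverse case.** Suppose each patient's true level is stable, both readings carry error, and X tracks the true level. The change score is then pure error and X is unrelated to it. Adding the noisy baseline brings in regression to the mean, and X becomes informative:

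| Reliability | r | n=30 without / with baseline | n=50 without / with baseline |
|---|---|---|---|
| 0.5 | 0.3 | 4.8% / 14.1% | 5.1% / 22.9% |
| 0.5 | 0.5 | 4.4% / 39.7% | 5.2% / 63.1% |
| 0.7 | 0.3 | 4.6% / 9.9% | 5.2% / 14.6% |
| 0.7 | 0.5 | 4.7% / 22.6% | 5.2% / 37.6% |
| 0.9 | 0.3 | 5.0% / 6.4% | 5.0% / 7.7% |
| 0.9 | 0.5 | 5.1% / 9.4% | 5.1% / 14.5% |

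**Step 4. Both mechanisms together.** Here trait-severity correlation is 0.5, severity explains 25-40% of true change, and both readings carry error:

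| Reliability | n=30 without / with baseline | n=50 without / with baseline |
|---|---|---|
| 0.95 | 19-27% / 5-6% | 30-44% / 5-6% |
| 0.85 | 13-18% / 7-8% | 19-27% / 9-10% |

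Over correlations of 0.3-0.5 and reliability of 0.85-0.99, including no dependence on severity, the overall ranges are about 5-32% (n=30) and 5-51% (n=50) without baseline, against about 4-10% and 4-16% with it. The upper ends are not bounds. With an error-free baseline, correlation 0.5 and a 40% share, the rate without baseline was 41% (n=30) and 63% (n=50).

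**Step 5. Requiring significance in both models.** The chance that X passes both cannot exceed the smaller of the two rates. That is about 5% in every row of steps 2 and 3, and at most about 10% in step 4.

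**The case against.** The strongest counter-argument is that adding baseline is not a clean repair. Step 3 shows that it can create the false predictor it is meant to remove. At reliability 0.85 with a stable true level and r=0.5, a separate check gave 5.6% without and 12.3% with baseline at n=30, and 4.6% and 18.6% at n=50. The documents hold nothing that decides between the two mechanisms. This stands, and it is why both fits are needed.

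Other parts of the objection also stand:

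- A reader might infer that the plan will report a confounder-adjusted edema reduction. It does not say so. The regressions are for "testing the effects of confounding factors including age, gender, BMI, foot insensitivity, etc", which concerns coefficients, and the reduction itself goes to the paired t-test. The confounder issue is therefore one of wording.
- A reader might infer that every regression term is a fixed trait. Activity is measured at baseline and 4 weeks (Section D), and ABI and SPP can also change. In the H2 paragraph the terms are called predictors; the word confounding reaches H2 only through the reused H1 plan.
- Baseline is unlisted rather than excluded. The H1 covariate list is open-ended, and the H2 plan borrows one containing ABI and SPP. The named predictor lists are closed, however, and an open-ended list does not prespecify baseline.
- A reader might infer that false predictors would shape the next trial. G1 says only that results will allow its sample size to be calculated.

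A separate matter lies in the same H1 sentence. The device is listed as a predictor although every patient receives it, so its coefficient cannot be estimated (six columns, rank five).

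**Conclusion.** The point holds as a minor one. The H1 and H2 predictor models omit from their lists the covariate most likely to explain change, and findings described as independent predictors could then reflect starting severity alone. Omission does harm only if change depends on baseline and the trait correlates with it. Under the assumptions in step 4 the false-positive rate without baseline then lies anywhere from nominal to about one in three at n=30 or one in two at n=50. If true change does not depend on baseline, omission costs nothing and inclusion costs a modest inflation at plausible reliability.

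The documents do not support the stronger readings that false predictors are inevitable, that the regressions are worthless, or that the test of mean edema reduction is compromised. All sizes rest on assumed correlations, reliability and strength of dependence. The analyses are exploratory and the study is a pilot.

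**What to change.** In G2:

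1. Add the outcome's own baseline value (edema measure, SPP or ABI) to each H1 and H2 predictor model.
2. Report the same model without baseline as a sensitivity analysis, and call a trait an independent predictor only if it holds in both.
3. Describe age, gender, BMI and foot insensitivity as exploratory effect modifiers of the within-patient change, not confounders.
4. State the time point of each predictor, and whether the rate of edema reduction is absolute or percent.

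The cost is wording, one extra fit per model and one degree of freedom. With four estimable predictors and an intercept, residual degrees of freedom fall from 30−5=25 to 24, or from 50−5=45 to 44. Requiring agreement between both fits also lowers the chance of detecting a real predictor, which is acceptable for exploratory work. No new data are needed.
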